Proud & Empowered! Intervention: The proposed study is intended to rigorously test the efficacy of Proud & Empowered! (P&E) program in a large-scale RCT with 24 high schools across the Greater Los Angeles Area. Schools will be randomly assigned to an intervention or control condition. Schools assigned to the intervention condition will be further randomized to receive either just the P&E direct intervention or both P&E and Make Space. Detailed information on each program (Proud & Empowered! and Make Space) can be found in sections below. LGBTQ participants in the intervention schools will participate in P&E, whereas those attending control schools will complete only study survey measures during the study on the same timeline (all three time points) as the intervention schools.

LGBTQ Youth Procedures: For LGBTQ P&E participants, measures (information on measures can be found in the *Instrumentation* section below) will be obtained at three time points: the beginning of the P&E intervention (September), after the intervention period (November), and at the conclusion of the school year (May). LGBTQ+ student participant survey can be found in the attachments section as "Y2 P&E Survey.docx". LGBTQ+ youth participants will create a Unique ID, which the study team will use to link measures taken over time. Detailed information on recruitment of LGBTQ youth participants can be found in the *Recruitment* section above. School counselor will ensure there is a time and space available for each student to meet for a 45-minute intervention session once per week for 10 weeks. The study activities will occur at the school during school hours and the school counselor will ensure students can discreetly participate in the intervention sessions by either 1) grouping participating youth into the same homeroom/advisory period where the intervention will administered by Study Facilitator/Study Coordinator, or 2) providing students with a counseling slip, allowing them to miss a class to

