A PDF of the Make Space intervention program can be found in the attachments section of this IRB application as "Make Space Curriculum.docx". The Make Space intervention is a student leadership and advocacy intervention training program. The training will be facilitated by MSWlevel staff and is completed over four, 45-minute sessions, similar to how the P&E intervention sessions will be run. The Make Space intervention includes modules on: Team Building, Exploring LGBTQ+ Issues, Capacity Building, and Youth Activism. LGBTQ youth who are part of the P&E intervention will take part in this training, as will the Make Space Allies who were nominated by the P&E intervention participants. After the training, ongoing intervention planning and organizing sessions will be facilitated by MSW-level study staff focused on planning the school climate project chosen during the Make Space training. To support youth in identifying a school climate project for their school, WUSTL study staff will provide participating youth with their schools' results of the policy scan. Youth will work with the WUSTL study staff as frequently as is needed to implement the chosen activities. Similar to the P&E Intervention implementation plan, study activities will occur at the school during school hours and the school counselor will ensure students can discreetly participate in the intervention sessions by either 1) grouping participating youth into the same homeroom/advisory period

where the intervention will administered by Study Facilitator/Study Coordinator, or 2) providing students with a counseling slip, allowing them to miss a class to participate in the intervention session. Schools will choose what works best for them. If option 2 is selected, Make Space sessions will be staggered and run during a different class period each week so that participating youth do not miss the same class every week. We have formalized the process for tracking fidelity and other outcomes after each session via a post-session facilitator feedback form. This form (uploaded to "attachments" section as "Post-Session Data Collection.docx) will be completed by the intervention facilitator ([name]) immediately after each session. Data to collect includes attendance (dosage), intervention location, and information on participant engagement and collaboration.

Instrumentation

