All measures are valid and reliable psychometric tests. As this is a quantitative study, all measures are closed-ended and survey-based. Information on each specific measure is as follows:

Sexual Minority Adolescent Stress Inventory: 54-item survey across 10 domains of minority stress. Assesses experiences of minority stress among adolescents. Each statement reflects past-30-day thoughts, feelings, and situations a person may have experienced.

Beck Anxiety Inventory: 21-item self-report assessment of anxiety symptoms.

PTSD Checklist for DSM-5 (PCL-5): 20-item self-report assessment of post-traumatic stress disorder (PTSD) symptoms which addresses all 20 DSM-5 symptoms of PTSD.

Beck Depression Inventory: 21-item self-report assessment of depression symptoms and severity of depression.

Adapted CSSRS Suicide Questions (Columbia Suicide Severity Rating Scale): Six items assessing current suicidality that were adapted from the longer, treatment-based Columbia Suicide Severity Rating Scale

Youth Risk Behavior Survey Substance Use Questions: Measures individual's usage of various substances in their lifetime and within the past 30 days as well as the ways in which individuals have used marijuana, tobacco, or nicotine in the past 30 days.

Coping Strategies Inventory: 16-item assessment measuring specific coping strategies people use in response to stressful events with each item assessing components of Problem Solving, Cognitive Restructuring, Social Support, Expressed Emotions, Problem Avoidance, Wishful Thinking, and Social Withdrawal.

LGBTQ+ Coping: 20-item assessment measuring ways individuals cope with stressors that are specifically related to being LGBTQ+ over the past 3 months.

California Healthy Kids Survey General Bullying and Gender Identity/Sexual Orientation-Based Harassment Module: Assesses students' perceptions of harassment experiences on school campus among the general student population in addition to bullying and harassment experiences on school campus specific of students who identify as, or are perceived to be, lesbian, gay, bisexual, transgender, questioning, or gender nonconforming.

Civic Measurement Models: Measures competency for civic action, political efficacy and participatory citizen to assess young people's perceived ability to engage in civic action (e.g., organize a meeting), express their political voice (e.g., sign a petition), and critically analyze political messages.

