Although the impetus for P&E is to reduce victimization and bullying experiences, increased visibility due to participation could result in increased targeting. This may not only occur for SGM-identified participants, but also for POL allies, who may be targeted by association. Given this, our recruitment and consent processes for both SGM and POL students will discuss this potential risk of participation. As part of our study intake procedures, we educate participants on existing policies and what procedures are in place to protect them, including whom they should contact and what kinds of support they can expect. During the intervention, facilitators check in weekly with participants about safety concerns and refer to school-based supports, as necessary, following existing school protocols. Youth may also discontinue participation, if desired, at any time. Finally, our DSMB will meet regularly to review all procedures, including potentially trial stopping factors such as increased victimization. These protocols allow us to monitor student experiences regardless of whether victimization experiences are related to study participation or other extraneous factors.

Suicide and Emergency Standards of Procedure

Potential Emergencies:

For purposes of monitoring and reporting adverse events, the following NIH definitions will be used:

Adverse Event (AE): any untoward medical occurrence that may present itself during treatment or administration of an intervention, and which may or may not have a causal relationship with the treatment. Adverse events could arise from the study (e.g., breach of confidentiality) or could arise due to the population under study (e.g., a participant becomes upset answering sensitive questions).

Serious Adverse Event (SAE): Any medical occurrence that results in death; is life-threatening; requires inpatient hospitalization or prolongation of existing hospitalizations; creates persistent or significant disability/incapacity, or a congenital anomaly/birth defect. Such an event could include suicidal ideation or attempted drug overdose or withdrawal, etc.

There are five possible sources of AE which we can foresee based on our prior work with sexual minority adolescents:

- 1. Emotional distress due to discomfort with the survey questions. Although rare, we recognize that some youth may find personal questions distressing to answer.

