Additional protocol for identifying suicidality in survey participants: Because the intervention participant surveys assess for recent suicidal ideation, intent, plans, and attempts, we will implement protocols to immediately identify youth who report suicidal risk and connect them to the school counselor. The participant survey will be programmed in Qualtrics and the final screen for all youth will instruct them to: "Let the research team know you've finished the survey to receive your gift card. Code: complete." This will allow the team to verify survey completion and give the student their gift card. The Qualtrics survey will be programmed to include the youth's score on the suicide measures with the "Code: complete" message, such that students with no risk will get "Code: complete 1" and those with highest risk will get "Code: complete 5." This code is designed to not catch the attention of the student, but still allow the research staff to note the student's risk level, and then confidentially connect the student to the school counselor for further help outside of the intervention session.

References:

- 2. D'Augelli A, Grossman, Arnold H. Disclosure of sexual orientation, victimization, and mental health among lesbian, gay, and bisexual older adults. *Journal of interpersonal violence*. 2001;16(10):1008-1027.

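### Harms between the November and May surveys: the 30-day minority-stress window covers only 14–20% of the interval, the suicide and bullying windows have no stated length, and other monitoring differs by condition

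*Protocol*

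**What the plan says.** **Risk and stopping.** Under *Data Safety Monitoring Board (DSMB)*, the Protocol says that greater visibility could bring more targeting, both of SGM participants and of allies. It says the DSMB will review "potentially trial stopping factors such as increased victimization", and that the procedures let the team follow what students experience whether or not it is linked to the study. The DSMB meets quarterly in the first year and annually after that.

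**Conditions and surveys.** Under *Methods*, schools are randomised to intervention or control, and intervention schools are randomised again to P&E alone or P&E plus Make Space. The cohort is surveyed in September, November and May. Control participants do the surveys and nothing else. LGBTQ youth in Make Space get no additional survey. Allies are surveyed in November and May.

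**Recall periods (Protocol, *Instrumentation*).** For the minority-stress inventory: "Each statement reflects past-30-day thoughts, feelings, and situations a person may have experienced". For suicidality: "Six items assessing current suicidality that were adapted from the longer, treatment-based Columbia Suicide Severity Rating Scale". The safety section instead says that "the intervention participant surveys assess for recent suicidal ideation, intent, plans, and attempts". No recall period is given for the California Healthy Kids bullying and harassment module.

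**Other monitoring.** Facilitators ask about safety every week while the intervention runs. After the four Make Space training sessions, staff-led planning sessions continue without a fixed schedule: "Youth will work with the WUSTL study staff as frequently as is needed to implement the chosen activities". The post-session form is said to record attendance, location, engagement and collaboration. There is also an adverse-event log, an emergency procedure, and a suicide-risk code shown when a survey is completed.

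**The concern.** The P&E sessions are arranged to be discreet. Make Space and the student-led school climate project come after them and are the visible part of the program. If visibility raises the risk of targeting, the time to watch is after the November survey. Yet no survey is scheduled between November and May, and the one victimization-related measure with a stated window looks back 30 days.

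What is at stake is the comparison of harms between conditions. A stopping factor such as increased victimization needs a comparator. In the Make Space schools, staff contact may bring events to light. In the control schools, nothing but the surveys is described. Unequal ascertainment can produce a false signal in the arm that is watched more closely. A May survey that does not ask about most of the interval can hide a real one.

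**Working it through.** The documents state no figure on this point, so there is none to reproduce. The check has three steps.

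**1. Share of the interval covered by a 30-day window in May**

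Inputs: recall window 30 days (*Instrumentation*); surveys in November and May, days not given (*LGBTQ Youth Procedures*). Taking the extreme dates in a non-leap year:

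- Shortest interval, 30 November to 1 May: 152 days.
- Longest interval, 1 November to 31 May: 211 days.
- Share covered = 30 / interval. Share uncovered = 1 − 30 / interval.

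| Interval | Covered | Uncovered |
|---|---|---|
| 152 days | 30/152 = 19.7% | 122/152 = 80.3% |
| 211 days | 30/211 = 14.2% | 181/211 = 85.8% |

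A leap year adds one day to each interval and leaves the range at 80% to 86%.

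For the September to November interval, the first and tenth weekly sessions are 9 × 7 = 63 days apart if no week is missed, and both are data-collection sessions. A 30-day window then leaves 33/63 = 52% uncovered. The gap is smaller, but it also exists at the November survey.

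**2. To which measures the figure applies**

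| Measure | Stated window | Uncovered share, November to May |
|---|---|---|
| Minority-stress inventory | 30 days | 80–86% |
| Suicide items | current, or recent | cannot be computed |
| Bullying and harassment module | none stated | cannot be computed |
| Substance use | lifetime and 30 days | 0% and 80–86% |
| LGBTQ+ Coping (Protocol only) | 3 months | about 40–57% |

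The last row uses 90 to 92 days: 1 − 92/152 = 39.5%, and 1 − 90/211 = 57.3%. The last two rows measure neither victimization nor suicidality, so their longer windows do not close the gap.

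**3. Monitoring between the November and May surveys, by condition**

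| Condition | What the documents describe |
|---|---|
| Control | Nothing scheduled |
| P&E only | Nothing scheduled after the ten P&E sessions |
| P&E plus Make Space | Four training sessions, then planning sessions as needed; check-ins while the intervention runs |

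The suicide-risk code appears only when a survey is completed, so it adds no screening between surveys. The adverse-event log depends on an event reaching staff, and staff contact differs by condition as the table shows.

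**The case against.** **The bullying module may already cover the interval.** It is the measure most directly about victimization. Its wording sits in a survey attachment that is not part of the two documents. If it asks about the whole period since November, the bullying part of the gap closes. The same is true of the suicide items if *recent* reaches back that far. This stands, and it is why the conclusion is conditional for those two measures and why the fix omits items already covered.

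**Monitoring exists where the visibility risk is greatest.** Make Space schools have continuing sessions run by MSW-level staff, and the emergency procedure and event log apply to disclosures throughout the study. This stands in part: events in those schools may well be caught. It does not help the comparison, because nothing equivalent is described for the other two conditions.

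**Lasting harm would show in May anyway.** The depression, anxiety and PTSD scales could carry a trace of an earlier event. That is so, but a symptom score does not identify a harassment episode or a suicide attempt.

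**Schoolwide data exist.** The combined protocol and SAP plans to obtain California Healthy Kids Survey data. They are anonymous, come from a third party and are analysed apart from all other study data, so they cannot show what happened to cohort members.

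**A retrospective block is late and imperfect.** The DSMB would learn of a January event only after the May survey. Participants also know their condition, and P&E sessions deal with peers and school stress, so labelling and reporting of harassment may differ by arm. Both points stand. They limit what the block can do but do not remove its value for the between-arm comparison.

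**Conclusion.** The concern holds in a limited form. In May the 30-day minority-stress inventory covers about 14% to 20% of the November to May interval. For suicidality and bullying, the documents do not say how much is covered. No structured ascertainment is described between those surveys for control schools, or for P&E-only schools after the ten sessions. A comparison of harms by condition would be incomplete and asymmetric.

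This rests on two assumptions: that the surveys fall on some day in the stated months, and that the unseen wording of the bullying and suicide items does not already span the interval.

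A reader might infer more than the documents support:

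- That 80–86% of the Make Space and project phase goes unobserved. The length and end of the project are not stated, so the figure is a share of the survey interval only.
- That the same figure applies to suicidality. *Current* and *recent* have no length in days.
- That 30 days and *current* are the only recall periods given. Substance use has lifetime and 30-day windows, and LGBTQ+ Coping has three months.
- That an event in mid-winter would leave no trace, or that the DSMB is blind. Check-ins, the event log or items of unknown window may catch some events.
- That targeting is the trial's main risk. The Protocol names it as a possible consequence of visibility and separately lists five foreseeable sources of adverse events.

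The change is worth making because it is cheap and uses surveys already scheduled in every condition.

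**What to change.** 1. State the recall periods of the bullying and harassment module and of the suicide items, and reconcile *current* with *recent*.
2. In the November and May cohort surveys, in every condition, add a short block after the existing scales, worded *since the last survey*: LGBTQ-related bullying or harassment, being outed, suicide attempt, overnight hospital stay. Omit any item whose existing wording already covers the whole interval.
3. Add the victimization items to the May ally survey, since the Protocol names allies as at risk. Allies exist only in Make Space schools, so these results are descriptive.
4. Report the cohort results to the DSMB by randomised condition. With 12 youths selected at each of 24 schools, the cohort is at most 24 × 12 = 288, so counts by condition are the sensible form.
5. Keep the 30-day inventory unchanged as the outcome measure.

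**Cost:** about four or five items, one DSMB table and a survey amendment. Recall over several months is less exact than over 30 days, and reporting may differ by arm because participants know their condition; the DSMB table should say so. The block supports the between-arm safety comparison and does not replace real-time detection. How answers to the new items feed the existing safety procedures is for the investigators to settle.

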To fill this gap, we have developed a first-of-its-kind school-based intervention for SGM youth, Proud & Empowered! (P&E). The multi-level program was developed over the last 9 years through (a) psychometric, developmental, and acceptability studies funded by the NIH, foundations (Zumberge), and intramural sources; (b) a collaboration with three SGM youth dropin centers, more than 100 SGM youth, and a dozen academic and clinical experts; and (c) an exploratory study (R21MD013971) to assess the feasibility and preliminary efficacy of the intervention. Given encouraging findings, we now propose to employ a large-scale randomized controlled trial (RCT) with 24 schools in Los Angeles to establish program efficacy. At intervention sites (n = 12), after the 10-session small group portion of the intervention with SGM youth is completed, peer allies (who are identified through a popular opinion leader model) are invited to participate in 4-session leadership program focused on changing SGM-related school climate. This is followed by student-led implementation of environmental change strategies at the school level focused on key domains of school climate described by Thapa et al. (2013): safety, relationships, teaching and learning, and institutional environment. At the SGM student

level, analysis will focus on the hypothesized mechanism of change (minority stress) and key behavioral health outcomes (depression, anxiety, PTSD, suicidality, substance use).

Change in school climate will also be assessed qualitatively using content analysis and observational methods in the intervention and post-intervention years. Our specific aims are to:
1) Determine participant-level efficacy of the intervention in an RCT with 24 schools, 2)
Determine the schoolwide intervention effects on (a) reporting of minority stress and behavioral health outcomes among all SGM students and (b) perceptions of school climate (norms, attitudes, beliefs, bullying behaviors toward SGM youth, policies) among all students, and 3)
Examine factors that may affect intervention success (e.g., fidelity of implementation, barriers or facilitators to implementation, school or student characteristics) to prepare the intervention for future dissemination.

Participants

1. Inclusion Criteria:

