Data Analysis

A series of analyses will be conducted to thoroughly investigate the program effects and its fidelity on outcomes of interest. First, a cluster-randomized repeated measures ANOVA will be used to examine the intervention effects on minority stress, behavioral health outcomes, and coping skills among the cohort of SGM adolescents who participate in the small group intervention and their control-school counterparts. Second, qualitative content and observational analysis by study staff will be used to conduct a baseline policy scan in the intervention year, inform Make Space participant activities, and evaluate change in policies over the course of the year.

Data Protection

All survey data will be coded using a unique code selected by each participant. Coded data will be held separately from all identifying data, such as recruitment information. Assent/consent will be collected in a separate survey though RedCap in order to keep as little identifying information about LGBTQ+ participants and POL participants as possible. All contact information used for recruitment be destroyed at the conclusion of the study. Downloaded data will be stored on dual-authentication and password-protected computers. Only the PI and authorized study staff will have access to survey data.

Dissemination of Findings

The proposed study plans to consistently disseminate findings from study data and – if warranted – to provide broad access to the final intervention program. The dissemination plan aims to inform research on minority health, risk and protective factors among SGM youth. Research findings will also be disseminated through peer-reviewed journals, national conferences, and relevant compendiums of intervention research if possible (e.g., Cochrane).

Data Safety Monitoring Board (DSMB)

The DSMB will meet quarterly during the first year of the project and annually thereafter and is composed of recognized experts in SGM clinical ([name]) and adolescent research ([name]; [name]) with no direct involvement in the study. The DSMB will be charged with ensuring the highest standards for participant safety and data

quality. Initially, the board will review the study design, instruments and methods, recruitment criteria, intervention plan, and data analytic plan. It will provide recommendations to safely achieve our goals. Subsequent meetings will focus on monitoring study participant enrollment, safety, and protocol adherence (*see DSMB and Letters of Support*).

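### Does leaving the coping outcome undefined, when LGBTQ+ Coping looks back 3 months, undermine the November coping result?

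*Protocol*

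**What the plan says.** The Data Analysis section of the Protocol states that "a cluster-randomized repeated measures ANOVA will be used to examine the intervention effects on minority stress, behavioral health outcomes, and coping skills" in the small-group cohort and its control-school counterparts. The Combined protocol and SAP carries the same sentence. Neither names an instrument there.

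For most outcomes the match is plain. Minority stress has one inventory in the Instrumentation section, and each of the "key behavioral health outcomes (depression, anxiety, PTSD, suicidality, substance use") in the Objectives has one measure. Coping has two in the Protocol. The Coping Strategies Inventory is a "16-item assessment measuring specific coping strategies people use in response to stressful events", with no recall period stated. LGBTQ+ Coping is a "20-item assessment measuring ways individuals cope with stressors that are specifically related to being LGBTQ+ over the past 3 months". The Combined protocol and SAP lists only the Coping Strategies Inventory.

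On timing, LGBTQ Youth Procedures sets the cohort's surveys at three points: "the beginning of the P&E intervention (September), after the intervention period (November), and at the conclusion of the school year (May"). Students attend a "45-minute intervention session once per week for 10 weeks", and the 10-week P&E Intervention Procedures place data collection in the opening and closing sessions. Control-school students "will complete only study survey measures during the study on the same timeline (all three time points) as the intervention schools".

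**The concern.** Two things look wrong. First, an outcome with two candidate scales and no stated choice could, in principle, be settled after the results are known. Second, if LGBTQ+ Coping is used, its November window opens before session 1. Weeks in which nobody had received the program would then count toward the November score in both arms, and the difference between arms could be understated. The program has a session on stress and coping, and November is the first measurement after it, so a reader would want that result to be interpretable. LGBTQ+ Coping is the only listed scale with a stated fixed recall period longer than the gap between the first two surveys.

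**Working it through.** The documents give no sample-size, power or dilution figure to reproduce. The check is calendar arithmetic followed by what can be inferred from it.

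**Step 1: the gap between surveys.** Sessions 1 and 10 are nine weekly intervals apart: 9 × 7 = 63 days. Ten full weeks give 70. Over all 30 × 30 = 900 pairs of September and November dates, the gap runs from 32 days (30 September to 1 November) to 90 days (1 September to 30 November).

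**Step 2: the look-back against the gap.** Days before baseline = look-back − gap, with the share of the window in brackets.

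| Reading of 3 months | Gap 63 | Gap 70 | Gap 90 |
|---|---|---|---|
| 90 days | 27 (30%) | 20 (22%) | 0 |
| 91 days | 28 (31%) | 21 (23%) | 1 (1%) |
| 92 days (calendar, from any November date) | 29 (32%) | 22 (24%) | 2 (2%) |

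The look-back exceeds the gap in all 900 pairs at 91 or 92 days. On a strict 90-day reading there is one tie.

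**Step 3: other scales and May.** The minority stress inventory asks about the past 30 days, which fits inside even the 32-day gap. The substance use questions cover "usage of various substances in their lifetime and within the past 30 days", so their lifetime items also reach before baseline. From 30 November to 1 May is 153 days in the 2023–24 school year, so the May window lies wholly after the 10-week program.

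**Step 4: from days to an effect on the estimate.** This needs assumptions that the documents do not supply.

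- *Recall weights.* Even weighting over 91 days puts 28/91 = 31% (gap 63) or 21/91 = 23% (gap 70) of the weight before baseline. Weight falling linearly to zero at 91 days puts (28/91)² = 9% or (21/91)² = 5% there. To read these as a loss from the full effect, that effect must also be complete and constant from session 1, yet session 1 is the introduction.
- *Power.* Assume a separate two-sided 5% test in November, 12 × 12 = 144 students per arm, a standardised effect of 0.4 and an intraclass correlation of 0.02. The effective number per arm is 144/(1 + 11 × 0.02) = 118 and power is 0.87. Multiplying the effect by 63/92 with the standard deviation held fixed lowers power to 0.56. If instead daily variation is independent and evenly weighted, the longer window also averages out noise. The squared signal-to-noise ratio of the change is then (63/91)² / [(2/91)(63/91)] = 31.5, identical to 1/(2/63) = 31.5 for two separate 63-day windows, so nothing is lost.

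The result runs from no loss to a material one depending on assumptions, so no single figure can be attached to the plan.

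**Step 5: two scales for one outcome.** With separate 5% tests and no true effect, the chance that at least one is significant lies between 5% (perfect correlation) and 1 − 0.95² = 9.75% (independence). The plan states neither the 5% level nor a separate November test, and two coping scales answered by the same students are unlikely to be independent.

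**The case for a change.** The strongest case for a change is that the remedy is cheap. One line naming the scale or scales would remove the chance of choosing after the fact, and one sentence on the overlap would help a reader interpret a small November effect. The factual base stands: the outcome is not mapped to an instrument, the two instrument lists differ, the look-back is longer than the scheduled gap, and carry-over would act toward no difference.

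Three things weaken it.

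- The analysis said to be harmed is not in the plan. Only a three-time-point ANOVA is specified, and neither document makes November the key comparison.
- The recall argument is a chain of conditions: LGBTQ+ Coping is analysed, the 3 months describe the coping rather than the stressors, and students give weight to the oldest weeks. The second turns on wording in a survey attachment that is not in the documents.
- Naming a scale would not close the choice of score. The Coping Strategies Inventory alone has seven named components.

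The differing lists may also reflect versions. The Protocol is dated August 2023 and refers to year-two files and a different university's staff, while the combined document as supplied has no date. That LGBTQ+ Coping was added later is an inference and cannot be proved from the text.

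**Conclusion.** No change to the plan follows. The missing mapping is a gap that analysts fill sensibly. The Protocol fields two coping instruments and says coping will be analysed, so the ordinary course is to analyse and report both, which leaves nothing to pick. The documents give no ground for preferring one scale over the other.

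The look-back is a property of the scale. On the session schedule it covers 21 to 28 pre-program days out of 91. That assumes surveys at sessions 1 and 10, a gap of 63 to 70 days, and the 3 months applying to the coping itself. Any consequence is confined to one scale at one of three time points, is shared by both arms, points toward no difference and does not extend to May. Its size is undetermined. A shorter recall period would trade one limitation for another and is a matter for the scale's design. Stating the scales and the actual survey dates belongs in ordinary reporting, and doing so would alter no estimate.
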